Mediated by a variety of molecules, there is an imbalance in the vascular tone favoring net vasoconstriction that mediates EIH. Animal studies unambiguously demonstrate the primary importance of CKD in the genesis of EIH. There is little evidence for EPO as a direct vasoconstrictor nor is there strong evidence for its effect on blood viscosity as a mechanism of EIH. However, preclinical studies show deranged regulation of NO, endothelins, prostanoids, and the sympathoadrenal and renin-angiotensin pathways as causes of EIH. Preliminary human studies suggest that EPO administration is also associated with enhanced vasoconstriction induced by catecholamines and angiotensin II; in addition, oxygen sensing by the vascular tissue may be deranged in those with EIH. EIH, at least in part, appears to be independent of an increase in Hgb because experiments show that Hgb may be raised by EPO without an increase in blood pressure (BP) by simply treating animals with EPO binding protein and that treatment with EPO in the setting of iron-deficiency may not raise Hgb but still increase BP. Finally, in rats with CKD, whereas EPO increases Hgb and BP, HIF stabilizers increase Hgb similarly but may actually reduce BP compared to placebo-treated animals. A review of the literature suggests an incomplete and poor understanding of the mechanisms of EIH. Better mechanistic designs are therefore needed, especially in patients with CKD, to dissect the precise mechanism of EIH.

OBJECTIVES AND HYPOTHESIS

Objectives

Primary Objective

To test the hypothesis that EPO treatment from baseline to 12 weeks in anemic patients with CKD and controlled hypertension will raise BP, we are performing a randomized control trial with a “waiting-list” design. After a 1-week run-in, we will randomize 160 participants into either the delayed start group, or the immediate start group.

If the time course, the magnitude, and the mechanisms of EIH, we will better be able to design studies to compare the vascular effects of EPO and HIF stabilizers in the future. Thus, this study has the potential of improving our understanding of a common side effect of EPO by precisely quantifying the

magnitude of BP change, its effects on endothelial function, and discovering the biomarkers of these adverse effects. Thus, we can in the future robustly compare these effects of EPO with HIF stabilizers.

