The first study to show that CKD was an important determinant of EIH was reported in 1995 ²³. In this study, male Wistar rats underwent subtotal nephrectomy at the age of 6 weeks to induce CKD. After 6 weeks of recovery, they were treated for 3 weeks with either vehicle or EPO; sham-operated animals who received EPO or vehicle served as comparators. Treatment with EPO provoked a significant increase in Hgb regardless of nephrectomy. Interestingly, EIH occurred only in the nephrectomized group; systolic BP increased by 37.5 ± 11 mmHg. In contrast, confirmed by a study in 1997 ²⁴, no significant increment was seen in systolic BP in the non-nephrectomized, sham- operated EPO-treated or vehicle-treated rats despite increase in Hgb.

Clinical observations are consistent with animal data. Although EPO is well known to be abused by athletes to enhance performance, we have not observed hypertension or hypertensive crises in this population. Similarly, the incidence of hypertension in zidovudine-treated HIV positive anemic patients or among those undergoing cancer chemotherapy is low. However, EIH is commonly reported among those with CKD, including those on dialysis ⁶. The implication of the above animal studies and human observations is that underlying CKD is necessary for EIH.

Hemopoietic versus hypertensionogenic effects of EPO

Animal experiments in general suggest that hypertension is not associated with an increase in Hgb ²⁵. If EPO is administered to anemic animals with CKD but Hgb is kept low by feeding an iron deficient diet, hypertension still occurs. Similarly, among patients on long-term hemodialysis, treatment with iron to increase Hgb is not associated with a parallel increase in BP ²⁶. The dose-response relationship of Hgb with EPO versus BP with EPO are different. For example, an increase in Hgb is dose-dependent, but an increase in BP is not ^{1,27}. Some studies, however, point to a direct relationship. For example, during the first 5 weeks of administration of erythropoietin, the change in Hgb concentration was directly related to an increase in diastolic BP ($r=0.42$, $p<0.001$) ³.

To understand the hypertensionogenic effects of EPO, consideration of the biology of the EPO receptor expressed in the hemopoietic and non-hemopoietic tissues is needed. Taken together, these data support the importance of the EPO receptor in the non-hemopoietic tissues in the genesis of EIH.

EPO-receptor and its relevance to EPO-induced hypertension

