On the other hand, HIF stabilizers may raise EPO to more physiologic levels, reduce crosstalk with vascular EPO-receptors, and mitigate hypertension. A 2014 study demonstrated in a rodent model that compared to EPO, treatment with HIF-stabilizer molidustat corrected anemia associated with subtotal nephrectomy. However, in contrast to EPO, molidustat reduced systolic BP in a dose-dependent manner⁸². The authors postulate that anti-inflammatory and anti-fibrotic effects of the drug on the kidney may be operative. This study further illustrates that increment in Hgb can be dissociated from an increment in BP. Human data are available but are thus far inadequate to address the question of risk for or protection from incident hypertension with HIF stabilizers ⁸³⁻⁸⁶.

RESEARCH PROTOCOL AND TRIAL DESIGN

Overall trial design and plan

To test the notion that EPO treatment in anemic patients with CKD and stage 1 or less hypertension that is treated or untreated with antihypertensive medications will raise BP, we propose a randomized controlled trial with a “waiting-list design” as shown in **Figure 2**. In this design, half of the patients are treated immediately with EPO and the other half are put on a waiting list for 12 weeks, after which they begin treatment. Ultimately, the waitlisted patients are exposed to the intervention, thus serving as their own controls. The design allows between-group comparison by comparing responses in the parallel groups over 12 weeks and within-group comparison for the waitlist group in the second 12 weeks compared to the first 12 weeks. Titration of the dose of EPO will occur every 4 weeks to manage anemia as detailed below. The effect of EPO on BP will be assessed by change in diastolic ambulatory BP measured over 24 hours at baseline and again at 12 weeks in both groups and at 24 weeks in the waitlisted group. At baseline and every 4 weeks thereafter, we will also evaluate changes in clinic BP and albuminuria. At baseline and 4 weeks after intervention, we will measure endothelial function, and collect blood for biomarkers. The biomarkers we will be analyzing are renin, aldo, ET-1, catecholamine, ADMA, and urine nitrates and nitrites.

Figure 2: Trial design and study process

Visit		1	2-3	4	5	6-7	8	9	10
Measurement		Consent	Baseline	Week 4	Week 8	Week 12	Week 16	Week 20	Week 24
PROC	FMD		x	x		DS	DS		
HTN	24h-ABPM		x			x			DS
	Clinic BP	x	x	x	x	x	DS	DS	DS
Labs	24h-urine		x			x			DS
	Blood labs*	x**	x	x	x	x	DS	DS	DS

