	UACR (x3)		x	x	x	x	DS	DS	DS
	Biomarkers		x	x		DS	DS		
Group	Immediate Start		x	x	x				
	Delayed Start		x	x	x	x	x	x	x

*CBC, Renal Panel, Ferritin, TSAT

** V1 if consent: CBC & eGFR panel

DS = Delayed Start ONLY

This is a two-arm, open-label, single-center, randomized controlled trial to understand the mechanisms of EIH. Participants will be randomized based on stratum of baseline level of urine albumin/urine creatinine ratios (UACR) measured on three consecutive days. The primary analysis will compare the 80 participants in the early start group to the 80 in the delayed start (DS) or waitlisted group over the first 12 weeks. All procedures will be performed as listed in the table based on study visit. Confirmatory analysis will compare the first 12 weeks to the next 12 weeks in the DS group. Accordingly, the study procedures labeled DS will be performed only in the delayed start randomized participants.

Study Intervention

Participants with CKD and anemia who meet the inclusion and exclusion criteria will be randomized to either the immediate or delayed start group. There are at least 7 study related visits in the early start group, and 11 in the waitlist group. Two consecutive days are needed to perform 24h ambulatory BP monitoring, which will be done twice in the immediate start group and 3 times in the delayed start group. Patients will receive oral iron (ferrous sulfate, 324 mg orally twice daily) if serum ferritin concentration is <100 ng/mL or transferrin saturation is <20%. If clinic BP exceeds either 179 mmHg systolic or 109 mmHg diastolic or if clinic BP raises by >20/10 mmHg compared to baseline, antihypertensive medication dose will be increased or a new antihypertensive will be added.

Participants will be identified in the renal clinic or the electronic medical record system based on estimated GFR and Hgb. At baseline, all participants will have 24-h urine Na measured to assess dietary Na intake.

Treatment Adherence

We recognize the limitations of syringe count, but we will assess treatment compliance with the study drug by performing a syringe count at each of the study visits.

Protocol for the management of anemia

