Darbepoetin will be self-administered subcutaneously at a starting dose of 0.45 µg/kg once weekly. Hgb will be targeted between 10-12 g/dL with a goal of at least 2 g/dL increment from baseline. If a patient's Hgb increases by 2 or more g/dL during any 4-week period, the darbepoetin dose will be decreased by 25%. If Hgb rise over 4 weeks is < 1g/dL and patient is not in target Hgb range the dose of darbepoetin may be increased by 25%. If Hgb change from baseline is between 1 - 2 g/dL the dose of darbepoetin will be maintained. If Hgb concentration increases to >12.0 g/dL, the drug will be withheld until Hgb concentration falls to <12 g/dL, at which time it may be restarted at a dose 25% lower than the previous dose.

In a Phase III registration trial of darbepoetin in CKD,⁸⁷ the median response time to increase in Hgb was 7 weeks. The response was defined as an increase in Hgb of ≥ 1 g/dL from baseline and Hgb ≥ 11 g/dL. The peak response was achieved at 13 weeks. Since we want to magnify the difference between groups, a 12-week treatment period appears appropriate. We expect about half of the participants to be treated for 24 weeks since the waitlisted group will be treated after 12 weeks.

Stop points

1. Stop point for severe anemia: If Hgb drops to <8 g/dL, waitlisted patients (delayed start group) will be started on EPO therapy without further delay. In the TREAT trial, where the rescue threshold was 9 g/dL, less than half (46%) of the patients in the placebo group needed at least one dose of EPO over the life of the trial ¹⁰. The target for rescue therapy is even lower in this trial and we do not expect many patients to be taken off the waitlist.

2. Stop point for uncontrolled hypertension: If clinic BP exceeds either 179 mmHg systolic or 109 mmHg diastolic, or rises by >20 mmHg/10 mmHg, antihypertensive medication dose will be increased, or a new medication added.

Safety Assessments and Variables

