Comparison of the cohort with these measurements will also be done to understand if the inferences based on the ambulatory BPs accurately reflect the differences between the treatment groups using the clinic BPs. Repeated measures mixed models (PROC MIXED in SAS) will be utilized to assess the overall differences between the treatment groups using the clinic BPs. Additional analyses will explore the nocturnal patterns between the groups in the ambulatory BPs as well as the pattern over time using circadian models of BP in each group.

Between-group changes in hypertension status from baseline to 12 weeks will be tested using logistic regression. Worsening of hypertension at any time point will be defined either as an increase in BP medication or an increase in seated clinic diastolic BP of ≥ 10 mmHg or systolic BP ≥ 20 mmHg. The McNemar test will be used to compare within-group change in hypertension status from 12w to 24 w to that in the control period of 0 to 12w.

To test the hypothesis that EPO is causal to EIH via worsening of FMD, we will evaluate changes from baseline in FMD. That is, we will test if the worsening is a mediation effect using the technique described by Judd and Kenny⁹⁶ and elaborated by MacKinnon⁹⁷. The technique, expanded here for more than one potential mediator employs three regression equations:

- A. $Y = \beta_0 + \tau X_p + \varepsilon$
- B. $X_i = \beta_0 + \alpha_i X_p + \varepsilon$
- C. $Y = \beta_0 + \tau' X_p + \beta_1 X_1 + \dots + \beta_i X_i + \dots + \beta_k X_k + \varepsilon$ for all mediators together,
or $Y = \beta_0 + \tau' X_p + \beta_i X_i \varepsilon$ for each mediator separately

Y is the outcome result (e.g., change in 24-hour diastolic systolic BP), X_p is the group (early vs delayed start) and X_i represent the k purported mediators. The total effect of the treatment on the outcome (measured by the coefficient, τ) is the sum of direct effect (τ') of the treatment and the mediated, or indirect, effects ($\alpha_i \beta_i$). Mediation is established when four conclusions are met: (1) the treatment predicts the outcome variable (supported by a test of statistical significance of τ in equation [A]); (2) the treatment causes the potential mediator (α_i is significant in [B]); (3) the mediator causes the

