outcome variable controlling for the group assignment (β_i is significant in [C] and $\tau' < \tau$, which provides evidence for mediation rather than suppression); and (4) the mediated effect is statistically significant. For mediators that satisfy conclusions 1 through 3, the significance of mediation (conclusion 4) will be determined via interval estimation of the mediated effect using the asymptotic variance derivation of Sobel ⁹⁸ since the outcomes are the continuous measures. Additional analyses that look at thresholds of change (binary: worsening of hypertension or not) will utilize bootstrapping methods and logistic regression. The proportion of the effect mediated is calculated as the ratio of the indirect effect to the total effect, or $\alpha\beta/\tau$.

The primary outcome for flow-mediated dilatation is change in FMD from baseline to 4 w in those treated with EPO compared to time controls. Predictors of this change will be baseline values of the following biomarkers: plasma ADMA, urine nitrate and nitrite, and plasma renin, aldosterone, and endothelin-1 and change from baseline to 4 w in the above biomarkers. In addition, the baseline FMD will be an independent variable. This analysis will use regression models similar to the above-listed analyses.

Pre-specified sub-group analyses for BP response

- Effect of age: The effect of age (e.g., 65 or more and <65) will be tested using interaction effects.
- Effect of volume overload: Volume overloaded subjects are more likely to show worsening EIH with EPO therapy. In people with volume overload, renin and aldosterone levels are expected to be low and 24-hour urine Na high. We will dichotomize the baseline levels of these markers and examine the outcome on ambulatory BP using interaction effects.

Safety analysis

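### The FMD mediation analysis leaves out hemoglobin change, so a hemoglobin-related BP rise can be credited to endothelial dysfunction if hemoglobin and FMD changes are negatively correlated within arms

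*Combined protocol and SAP*

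**What the plan says.** The mediation paragraphs of the Analysis section (after Accounting for missing data) state the aim: "To test the hypothesis that EPO is causal to EIH via worsening of FMD, we will evaluate changes from baseline in FMD". Three regressions follow. Equation A regresses the BP change on group. Equation B regresses a mediator on group. Equation C regresses the BP change on group and mediator, either with all mediators together or with one at a time. The mediators are described only as variables that "represent the k purported mediators"; no list is given. Mediation is declared when four conditions hold: group predicts BP, group predicts the mediator, the mediator predicts BP given group with a direct effect smaller than the total effect, and the Sobel interval for the indirect effect excludes zero.

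The model for FMD change uses baseline FMD and baseline values of "plasma ADMA, urine nitrate and nitrite, and plasma renin, aldosterone, and endothelin-1 and change from baseline to 4 w in the above biomarkers". Outcome Variables item 4 gives the same biomarkers. Hgb is in neither place, nor in the primary mixed models or the subgroup analyses.

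Elsewhere the plan makes Hgb a treatment target: "Hgb will be targeted between 10-12 g/dL with a goal of at least 2 g/dL increment from baseline" (Protocol for the management of anemia), and "Titration of the dose of EPO will occur every 4 weeks to manage anemia as detailed below" (Overall trial design and plan). The footnote to Figure 2 defines the blood labs as "CBC, Renal Panel, Ferritin, TSAT". They are scheduled at baseline and weeks 4, 8 and 12 in both arms.

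The background points both ways. The introduction holds that "EIH, at least in part, appears to be independent of an increase in Hgb". The section on hemopoietic versus hypertensive effects mostly agrees, but also cites a study in which "the change in Hgb concentration was directly related to an increase in diastolic BP" (r = 0.42, p < 0.001, first 5 weeks of treatment). The reference list shows that this study was in hemodialysis patients.

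**The concern.** Randomization protects the total effect in equation A and the group effect on FMD in equation B. It does not protect the FMD-to-BP slope in equation C, which is estimated from differences between patients in the same arm. If patients with a larger Hgb rise tend to have both a larger BP rise and a larger FMD fall, that slope is non-zero even when FMD has no effect on BP, and the third condition reads it as causation.

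What is at stake is the mechanism claim. A positive FMD mediation result could not be told apart from a hemoglobin-related one. That matters for the later comparison with HIF stabilizers, because the background stresses that a rise in Hgb and a rise in BP can be dissociated.

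**Working it through.** **Inputs from the plan.** SD of 24-hour diastolic change 10.3 mmHg; target difference 5 mmHg; 68 completers per arm; SD of FMD change 0.93%; detectable FMD change 0.45%; r(Hgb, diastolic BP) = 0.42.

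**Assumptions.** Two-sided 5% level (not stated); within-arm r(Hgb, FMD) of 0, -0.2, -0.3 or -0.4 (not given anywhere); r(Hgb, BP) = 0.2 as a lower alternative; FMD shift of 0.45%, or one SD (0.93%); linear effects and normal errors.

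**The plan's own figures reproduce.** n per arm = 2 × (1.96 + 0.8416)² × 10.3² / 5² = 66.6. The t-test version gives 67.6, hence 68. 68/0.85 = 80. Detectable FMD change = 2.80 × 0.93 × √(2/68) = 0.447%, or 0.450% with the t distribution, against 0.45% stated.

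**Size of the false indirect effect.** With no FMD effect, the FMD-BP correlation given group is r(Hgb, BP) × r(Hgb, FMD). At 0.42 and -0.3 it is -0.126. The slope in equation C is then -0.126 × 10.3/0.93 = -1.40 mmHg per 1% FMD. Multiplied by the group effect on FMD:

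- Shift of -0.45%: 1.40 × 0.45 = 0.63 mmHg, 13% of 5 mmHg.
- Shift of -0.93%: 1.40 × 0.93 = 1.30 mmHg, 26% of 5 mmHg.

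At a correlation of 0 the effect is 0. At -0.4 it is 0.84 mmHg (17%) and 1.73 mmHg (35%).

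**How often mediation is falsely declared.** Equations A to C were simulated with 68 per arm, a total effect of 5 mmHg, no FMD effect, and all four conditions applied, including the Sobel test. The runs also assumed a Hgb shift of 2 g/dL with SD 1 g/dL. The false indirect effect depends on neither, because the total is fixed at 5 mmHg and group is in equation C.

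| r(Hgb, BP) | FMD shift | r(Hgb, FMD) = 0 | -0.2 | -0.3 | -0.4 |
|---|---|---|---|---|---|
| 0.42 | 0.45% | about 1% | 4% | 9% | 16% |
| 0.42 | 0.93% | about 2% | 11% | 21% | 36% |
| 0.2 | 0.45% | about 0.5% | 1% | 2% | 4% |
| 0.2 | 0.93% | about 1% | 5% | 7% | 10% |

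Repeat runs agreed to within about one percentage point. With Hgb change added to equation C, the false indirect effect is about 0 mmHg and all four conditions are met in about 1-3% of runs in every scenario.

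**One coefficient is not the whole test.** The FMD slope alone is significant in about 16% / 31% / 50% of trials at r = 0.42 and correlations of -0.2 / -0.3 / -0.4 (Fisher z, 136 completers). The four-condition rates in the table are lower and are the relevant ones.

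**The case against.** The strongest objection is that the deciding input is missing. Equation C conditions on group, so there is bias only if Hgb and FMD changes are also correlated within arms, and no such correlation is reported. It could be zero, or run the other way. Under Nitric oxide, the background describes mice with a hematocrit of 80% and a compensatory increase in endothelium-dependent vasodilatation. A positive correlation would hide FMD mediation and tend to fail the condition that the direct effect be smaller than the total. This stands: the bias is possible, not shown.

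The value 0.42 is also a loose fit. It comes from hemodialysis patients over 5 weeks, and the plan does not say that it is a within-arm figure or that it applies to 12-week ambulatory BP in non-dialysis CKD. Hence the lower alternative of 0.2, where the rates are modest.

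Timing weakens the link further. FMD change is read at week 4, while the plan cites a median Hgb response time of 7 weeks and a peak at 13. This makes a strong week-4 correlation less likely but does not exclude one. It also means that week-4 Hgb only partly captures the Hgb rise acting on week-12 BP.

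Finally, the mediator list is open, so Hgb is unnamed rather than excluded. That is true but does not settle the matter. An unlisted mediator is not prespecified, and the one-at-a-time form of equation C would leave Hgb out of the FMD model even if it were listed.

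A reader might infer that Hgb is the main rival explanation, or that separating it from the vascular route is the trial's central question. The documents do not support either. They largely discount Hgb and viscosity, name several other pathways, and make the diastolic BP change the primary objective.

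**Conclusion.** The omission is certain from the text; its effect is conditional. Over the assumed range, false FMD mediation is declared in about 1% to 16% of trials for an FMD shift of 0.45% and 2% to 36% for 0.93%, if r(Hgb, BP) is 0.42. If it is 0.2, the ranges are about 0.5% to 4% and 1% to 10%. At zero Hgb-FMD correlation there is no bias.

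Two stronger readings should be resisted. The single-slope figures of 16%, 31% and 50% are not false-mediation rates, because the plan requires all four conditions. And the primary conclusion on diastolic BP is not in doubt: that comparison is randomized and does not use the mediation model. Only the mechanism claim is weakened. Since the plan itself targets Hgb, measures it and cites evidence linking it to BP, the analysis should include it.

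**What to change.** In the mediation paragraphs of the Analysis section:

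1. List the mediators.
2. Fit equation B for Hgb change from baseline to week 4, and include that change beside FMD change in the joint form of equation C. Week 4 matches the timing of FMD.
3. Repeat with week-12 Hgb change as a sensitivity analysis, because the cited response times put most of the Hgb rise after week 4.
4. Add baseline Hgb and its week-4 change to the predictors of FMD change, here and in Outcome Variables item 4.
5. Report the FMD indirect effect with and without Hgb. Claim a hemoglobin-independent vascular mechanism only if the effect persists with Hgb in the model.
6. State the remaining assumption of no unmeasured confounding between mediator and BP, and that Hgb may itself act through FMD, in which case FMD is still a genuine mediator.

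The cost is SAP wording and one extra term; no visit or assay is added. The FMD indirect effect may be slightly less precise. At a Hgb-FMD correlation of -0.4, the variance of the FMD slope rises by at most a factor of 1/(1 - 0.16) = 1.19, so its standard error rises by about 9%, before any gain from the BP variance that Hgb explains.

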Harms will be assessed by monitoring changes in weight, eGFR, CBC, clinic BP, and ABPM. For more definitive assessments, including hospitalizations, serious adverse events will be properly completed and sent to the VAMC DMC as requested. Safety of continued participation will be assessed at each study visit. The stop-points will be treatment-emergent severe adverse events that precludes further exposure to the drug, such as an allergic drug reaction, initiation of renal replacement therapy, or death. If the study drug is stopped, the subject will be continued to be studied so as to not violate the intention-to-treat principle.

Participants

Inclusion Criteria

- Stage 3 or 4 CKD defined as eGFR <60mL/min/1.73m² for ≥3 months or persistent albuminuria for ≥3 months; (i) urine albumin to creatinine ratio of more than 30 mg/g; (ii) urine protein to creatinine ratio of more than 150 mg/g; or (iii) at least 1+ dipstick positive proteinuria. ⁸⁸
- 24h ABPM <140/90 mmHg at baseline in the presence or absence of antihypertensive treatment.
- Hgb between 8 and 10 g/dL.
- No treatment with ESA within the previous 3 months.
- Adults, age 18 and older.

Exclusion Criteria

- Need for packed RBC transfusion in the previous 2 months.
- Myocardial infarction, stroke, or hospitalization for heart failure in the past 2 months.
- In the assessment of the investigator, have hematologic, inflammatory, infectious, or other conditions that might interfere with the erythropoietic response.

Retention of Participants

For half of the participants, only 7 visits are needed. For the others, at least 11 visits over 24 weeks of the trial are needed. We will offer \$20 per visit for participation in the trial to offset travel and time costs.

METHODS

Method of Randomization

Participants will be randomized in a 1:1 ratio to either early or delayed treatment (“waitlisted group”) with EPO according to UACR strata. A random permuted block design will be used to avoid imbalance in assignment to the treatment groups over time. A randomization sequence will be generated by the statistician and individually concealed in sequentially numbered opaque envelopes. After confirming eligibility with the principal investigator, the study pharmacist will dispense EPO according to the randomization sequence.

Measurement of clinic BP

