2. Change from baseline to 12 weeks in systolic BP in the comparisons above. Between group change in hypertension status from baseline to 12 weeks. Worsening of hypertension at any time point will be defined either as an increase in BP medication or an increase in seated clinic diastolic BP of ≥ 10 mmHg or systolic BP ≥ 20 mmHg. Within-group change in hypertension status from 12w to 24 w will be compared to the control period of 0 to 12w in the delayed start group.
3. The primary outcome variable in this aim is to examine the change in FMD from baseline to 4 weeks in those treated with EPO compared to the waitlisted group. The hypothesis being tested is that EPO will cause impairment in endothelial function. Accordingly, those on EPO will have worsening of FMD.
4. The primary outcome variable in this aim is to examine the predictors of change in FMD from baseline to 4 w in those treated with EPO compared to time controls. Predictors of this change will be baseline values of the following variables: ADMA, urine nitrate and nitrite, renin, aldosterone, and plasma endothelin-1 and change from baseline to 4 w in the above variables. This analysis will answer the question: which of the pathways independently is predictive of endothelial dysfunction?

Sample Size

The primary objective of the study is to assess the change from baseline to 12 weeks in diastolic BP in EPO treated patients compared to controls. In the waitlisted group, we will measure the change from 12 weeks to 24 weeks compared to the change from 0 to 12 weeks. We have measured 24h

ambulatory BP in 183 CKD patients 4 weeks apart. The mean diastolic BP at baseline was 68.3 mmHg and at 4 weeks 68.1 mmHg. The mean difference was 0.14 mmHg and the standard deviation of the difference was 10.3 mmHg. With these assumptions, two-tailed tests and 80% power, the required sample size to detect a between-group difference of 5 mmHg is 68 subjects completing the study in each group. Assuming 85% of those randomized complete the trial, we would need to randomize $68/0.85 = 80$ subjects per group, or 160 subjects in total.

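### The four-condition mediation rule cannot tell worsening FMD raising BP from an early BP rise worsening FMD, so meeting it does not establish mediation

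*Combined protocol and SAP*

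**What the plan says.** The Hypothesis section expects the 12-week diastolic BP increase to be related to FMD worsening over the first 4 weeks. The Analysis section sets the aim: "To test the hypothesis that EPO is causal to EIH via worsening of FMD, we will evaluate changes from baseline in FMD". It uses three regressions: BP change on group (A), mediator on group (B), and BP change on group plus mediator or mediators (C). Mediation counts as established when the group effect on BP, the group effect on the mediator, the mediator coefficient in C (with a reduced group effect) and the Sobel test of the indirect effect all support it.

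Figure 2 fixes the timing. In the parallel comparison FMD is measured in both groups at baseline and week 4, and ambulatory BP at baseline and week 12. Clinic BP is taken more often: "At baseline and every 4 weeks thereafter, we will also evaluate changes in clinic BP and albuminuria". The plan uses clinic BP for imputing ambulatory BP, for repeated-measures models, for confirmatory analyses and for hypertension status. It does not link clinic BP to the FMD mediation test.

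**The concern.** Measuring FMD at week 4 and BP at week 12 looks like a time order. But the outcome is a change from baseline, so a BP rise already present at week 4 is part of it. If that rise impairs FMD, patients with the larger early rise have the larger FMD fall and, because BP changes persist, the larger 12-week BP change. Equation C then gives a significant mediator coefficient although FMD has no effect on BP.

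Randomization protects the group effects in A and B. It does not protect the mediator coefficient in C, which the plan reads as the mediator causing the outcome. At stake is the trial's main mechanistic conclusion, which could be reported with the arrow reversed.

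**Working it through.** **The plan's own figures.** The inputs are in Sample Size: "With these assumptions, two-tailed tests and 80% power, the required sample size to detect a between-group difference of 5 mmHg is 68 subjects" in each group, and "the standard deviation of the difference was 10.3 mmHg". Alpha is not stated; 0.05 two-sided is assumed.

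- n per group = 2 × (1.960 + 0.842)² × 10.3² / 5² = 66.6, so 67. The t-based solution is 67.6, so 68, as stated. 68/0.85 = 80, as stated.
- Detectable FMD change = 2.802 × 0.93 × √(2/68) = 0.447%, against the stated 0.45%.

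The plan gives no figure for the mediation analysis.

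**Reverse-direction model (FMD has no effect on BP).** There are 68 per arm and a 5 mmHg EPO effect. BP change has SD 10.3 at weeks 4 and 12, with within-arm correlation ρ between them. FMD change has SD 0.93% and within-arm correlation −r with week-4 BP change. d is any direct EPO reduction of FMD. The values of r, ρ, d and the share of the rise present at week 4 are assumptions.

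With s = r × 0.93/10.3 and the full rise at week 4, the equations estimate:

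- group effect on FMD: α = −(d + 5s)
- mediator coefficient: β = −ρ × r × 10.3/0.93
- apparent mediated share: αβ/5

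For r = 0.5 and ρ = 0.7: s = 0.0451, β = −0.35 × 11.08 = −3.88 mmHg per 1% FMD.

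- d = 0: α = −0.226, share = 0.226 × 3.88/5 = 0.17.
- d = 0.45 (the plan's detectable change): α = −0.676, share = 0.676 × 3.88/5 = 0.52.

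The true mediated share is zero in both cases.

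**Simulated percentage of trials meeting all four conditions:**

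| Setting (no FMD effect on BP) | r = 0.3 | r = 0.5 | r = 0.7 |
|---|---|---|---|
| EPO affects FMD only through BP, full rise by week 4 (ρ 0.3–0.7) | 0.5–3% | 2.5–18% | 13–42% |
| Plus direct EPO effect on FMD of 0.45% (ρ 0.5–0.7) | 21–40% | 57–76% | not run |

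With half the rise at week 4 and no direct effect, the range over all r is 0.1–14%. With no FMD–BP link it is 0–0.4%.

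**Can the rule see direction?** A true forward chain (FMD to week-4 BP to week-12 BP) with matched correlations passes as often as the reverse chain: 19% v 19% at r = 0.5 and 43% v 43% at r = 0.7 (ρ = 0.7). This is expected, because both chains imply the same joint distribution of group, FMD change and 12-week BP change.

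**Does week-4 clinic BP settle it?**

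- *Added to equation C* (r = 0.5, ρ = 0.7, d = 0.45): the false pass rate falls from about 76% to 1%, 23% or 49% at clinic BP reliability 1.0, 0.7 or 0.5. With d = 0 it falls from about 18% to 0%, 3% or 7%. But the true forward chain also falls, from 19% to 0.2%.
- *Lagged regression* of week 4-to-12 clinic diastolic change on group and 0–4 week FMD change (assumed clinic noise SD 5 mmHg, direct FMD fall 0.6%, true effect 2–4 mmHg per 1% FMD): power is 84–100% if the whole effect comes after week 4, 32–86% if half does, and about 3% if none does. With an assumed 8 mmHg treatment-induced drop after a diastolic rise above 10 mmHg, the half-early powers fall from 32% to 18% and from 86% to 53%. Under reverse causation, false positives are at most 5% when individual responses do not vary. They reach 6–46% when individual responses keep growing after week 4, depending on the assumed spread.

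**The case against.** The best defence has four parts.

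- **The order is pre-specified and early BP is looked at.** The clinic BP mixed models would show an early group difference. This stands in part: nothing carries that result into the mediation conclusion, and a group difference alone does not say whether BP drove FMD.
- **This is a general limit of mediation with a non-randomized mediator.** It stands. A reader might infer that the fault is simply leaving week-4 clinic BP out of equation C, and that adding it would fix direction. The documents do not support that: clinic BP and FMD are both week-4 measurements, so adjustment cannot order them.
- **An early rise is not shown.** The Background says that "during the first 5 weeks of administration of erythropoietin, the change in Hgb concentration was directly related to an increase in diastolic BP". A reader might take this as proof of a BP rise by week 4. It is a correlation (r = 0.42) with hemoglobin change, with no mean rise, from a study in hemodialysis patients, whom this trial chose not to study. It makes an early rise plausible and no more.
- **The false-mediation rates rest on assumed inputs.** This stands, and the low end is reassuring.

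A reader might also want the lagged regression as a condition for claiming mediation. It cannot serve as one. It misses an effect complete by week 4, and the antihypertensive increases described under Study Intervention and Stop points act on its outcome.

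**Conclusion.** The point holds in limited form. The four conditions show a pattern compatible with either direction, so the plan's statement that they establish mediation goes too far. The false-mediation rate with no FMD effect on BP ranges from at most 3% (r = 0.3, EPO acting on FMD only through BP) to about 40–75% (strong link with the full rise by week 4, or a direct EPO effect on FMD). The documents give neither the FMD–BP correlation nor the week-4 share of the rise, so no single rate can be defended, and false mediation cannot be called likely on the documents alone. What does not depend on the rate is that matched forward and reverse chains pass equally often. The comparison of 12-week diastolic BP between groups is not affected.

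**What to change.** Keep equations A–C. Replace the statement that mediation is established with: *consistent with mediation; direction not established by equations A–C alone*. Pre-specify three supportive analyses, none of them a gate:

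1. Week 4-to-12 clinic diastolic BP change regressed on group and 0–4 week FMD change.
2. Equation C with the week-4 clinic diastolic BP change added.
3. The reverse model, with week-4 clinic diastolic BP change as mediator of the group effect on FMD change.

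Report antihypertensive changes in weeks 4–12 alongside these. State in advance what counts as agreement: in (1) a larger FMD fall goes with a further BP rise, in (2) the FMD coefficient persists, and in (3) week-4 BP does not account for the FMD difference. Claim support for the FMD-to-BP direction only if they agree. Otherwise report an association with direction unresolved, which is not the same as refuting the FMD pathway.

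State the downsides in the SAP. Analysis (1) misses an FMD effect complete by week 4, is weakened by antihypertensive increases, and can be falsely positive if individual BP responses keep growing. Analysis (2) corrects only partly because clinic BP is noisy, and it also removes a true path running through week-4 BP. The cost is SAP wording and three regressions on scheduled data, with no new visits or measurements.
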